9.1.3 Strengths of study design

This is a prospective, non-interventional, multi-center, single arm cohort study of CRPC patient with bone metastases who will receive Radium-223 from routine clinical practice settings. This study will include patients in a real life scenario and thus from a more diversified and less selected patient population than in a clinical trial setting, using fewer eligibility criteria to be as much representative to the general CRPC patients with bone metastases as possible.

9.2 Setting

The study will be conducted in nuclear medicine clinics and practices throughout Germany. Data will be collected from approximately 300 patients. The observation period for each patient enrolled in this study is the time from start of therapy with Radium-223 until death, withdrawal of consent, loss to follow-up or regular end of the study which is defined as two years after the last administration of Radium-223 (whatever comes first in time).

9.2.1 Eligibility

Male patients with a diagnosis of CRPC with symptomatic bone metastases without known visceral metastases will be enrolled after the decision for treatment with Radium-223 has been made by the attending physician according to his/her medical practice.

9.2.2 Inclusion criterion/criteria

- Male patients diagnosed with CRPC with symptomatic bone metastases without known visceral metastases
- Decision to initiate treatment with Radium-223 was made as per investigator's routine treatment practice.
- Signed informed consent

9.2.3 Exclusion criterion/criteria

- Patients participating in an investigational program with interventions outside of routine clinical practice

9.2.4 Withdrawal

Each patient has the right to refuse further participation in the study at any time and without providing any reasons. A patient's participation is to be terminated immediately upon his/her request. While fully respecting the patient's rights, the investigator should seek to obtain the reason and record this on the Case Report Form (CRF).

In this observational study, withdrawal from the study is independent of the underlying therapy. On the other hand, premature end of therapy does not automatically imply end of documentation: Without withdrawal from the study, follow-up after end of therapy continues for two years, until death or until loss to follow-up (whatever comes first in time).

9.2.5 Replacement

Patients will not be replaced after drop out.

9.2.6 Representativeness

No further selection than outlined in Sections 9.2.1 – 9.2.3 should be made and patients should be enrolled consecutively in order to avoid any selection bias. With respect to site selection this study could have potential limited representativeness (at convenience sample) as we would be looking for sites with Radium-223 availability (nuclear medicine licensed facility) and experience with prostate cancer management and treatment. Currently, there are 105 nuclear medicine licensed facilities in Germany (August 2014). For sites participating in the study it is planned to include 8 to 10 patients per site.

9.2.7 Visits

Information on the patients, outcomes and other variables is recorded using Electronic Data Capture (EDC) by the treating physician (nuclear medicine physician or any other physician licensed in the administration of radioisotopes) or designated medical person at different time points. After the patient and treating physician have agreed on a treatment decision, the patient is informed about the study and has to sign an informed consent in order to participate. Baseline information is recorded with the status before the first Radium-223 administration during patient visit. For each treatment cycle, information from patient medical records is documented and entered to EDC system by the physician or designated medical person. These visits occur during routine practice, the study protocol does not define exact referral dates.

Baseline/First treatment visit

Once a patient is found eligible for inclusion, the investigator will inform the patient about the study. This will include discussing the consent form and asking the patient to read and – when agreeing to participate – sign the informed consent.

Typical information to be collected at the baseline/first treatment visit includes:

- Date of first treatment visit
- Demography
- Vital signs
- Medical history
- Prostate cancer history
- Concomitant diseases
- Opioid use and other concomitant medication
- Concomitant anti-cancer therapy
- WHO pain score
- ECOG status
- Bone scan
- Patient questionnaires on pain (BPI-SF) and QoL (FACT-BP), filled out by the patient prior to the first injection of Radium-223
- Laboratory parameters including ALP, PSA, and blood counts
- Dose of Radium-223 administered
- Adverse Events

Further treatment visits

Further treatment visits occur during routine praxis, typically every four weeks according to the approved label of Radium-223. Information to be collected at further treatment visits includes:

- Date of treatment visit
- Patient questionnaires on pain (BPI-SF) and QoL (FACT-BP), filled out by the patient prior to each injection of Radium-223
- Dose of Radium-223 administered
- WHO pain score
- ECOG status
- Changes in pain medication or other concomitant medication
- Changes in concomitant anti-cancer therapy
- Bone Scan, if available

- Laboratory parameters including ALP, PSA, and blood counts
- Adverse events
- Symptomatic skeletal events

Follow-up visit after end of treatment

If within routine clinical practice, data will be collected from a follow-up visit approximately one month after end of treatment. Typical information to be collected at this follow-up visit after treatment includes:

- Date of visit
- Patient questionnaires on pain (BPI-SF) and QoL (FACT-BP) filled out by the patient
- WHO pain score
- ECOG status
- Changes in pain medication
- Changes in anti-cancer therapy
- Bone Scan, if available
- Laboratory parameters including ALP, PSA, and blood counts
- Adverse events up to 30 days after last treatment
- Symptomatic skeletal events

Long-term follow-up

For long term follow-up either the patient or treating physician can be contacted by phone, mail or email every three months after end of treatment until death, patient's withdrawal, loss to follow-up, or end of study (whatever comes first in time) for a maximum of two years. Typical information to be collected at long-term follow-up includes:

- Date of follow-up
- Survival status
- Opioid use after last administration of Radium-223 yes/no, if yes, date of first use (only in patients without prior opioid use)
- Symptomatic skeletal events
- Further anti-cancer therapy

End of Observation

The reason for end of observation is documented which could occur at end of study, if the patient died, withdrew his consent or is lost to follow up. In case of death date of death and primary cause of death have to be documented.

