8.2 Secondary objective(s)

The secondary objectives in this study are:

- To evaluate the change of pain and bone pain related quality of life over time during treatment phase.

- To evaluate pain control rate.
- To evaluate pain progression rate
- To evaluate time to first pain progression.
- To evaluate time to first opioid use.
- To evaluate covariates on pain response of mCRPC patients during treatment phase.
- To evaluate pain response related to the extent of bone metastases at baseline
- To evaluate the relation between bone uptake in known lesions and pain palliation (only in patients with bone scan prior to start of treatment and a second scan during or within 6 weeks after end of Radium-223 treatment).
- To evaluate Radium-223 treatment patterns
- To evaluate the course of blood counts in patients with different extent of disease and in the whole patient population.
- To determine treatments and time to subsequent mCRPC treatment (TTNT).
- To determine the time to first symptomatic skeletal event (SSE).
- To determine overall survival (OS).
- Treatment-emergent adverse events (TEAE) (up to 30 days after last administration of Radium-223).

9 Research methods

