9.3 Variables

The investigator collects historic data (demographic and clinical characteristics) from medical records if available, or else by interviewing the patient. Likewise, the investigator collects treatment related data during treatment visits and follow-up visits. The investigator documents the study-relevant data for each patient in the case report form (CRF). The CRF is available upon request (see Table 4: List of stand-alone documents, Annex 1)

Table 2: Tabulated overview on variables collected during the study

Variables	Baseline and first treatment	Further Treatment visits	Follow-up after end of treatment	Long-term follow-up	End of observation
Date of visit	X	X	X	X	X
Patient informed consent	X				
Demography	X				
Vital Signs	X				
Co-morbidities (medical history, concomitant diseases)	X				
Prostate cancer history (initial diagnosis, diagnostic and therapeutic procedures)	X				
WHO pain score	X	X	X		
Performance Status (ECOG)	X	X	X		
Questionnaires BPI-SF and FACT-BP	X	X	X		
Location of bone pain	X	X	X		
Number and location of skeletal lesions (bone scan)*	X	X	X		
Exposure/treatment (dose of Radium-223)	X	X			
Concurrent diagnostic and therapeutic procedures for mCRPC	X	X			
Laboratory parameters including ALP, PSA, blood counts	X	X	X		
Opioid use	X	X	X	X***	
Concomitant medication	X	X			
Adverse Events	X	X	X**		
Symptomatic skeletal events		X	X	X	
Further treatment for mCRPC		X	X	X	
Survival assessment				X	
Reason for end of observation					X

*If available, an additional bone scan together with an assessment of bone uptake of Radium-223 can be documented independently from visits.

**Up to 30 days after last treatment with Radium-223.

***Only opioid use yes/no and date of first use

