9.4 Data sources

The investigator collects historic data (demographic and clinical characteristics) from medical records if available. Likewise, the investigator collects treatment related data, results of tumor assessments and other disease status information, also documented in the medical record, during visits that take place in routine practice. For patient reported outcomes questionnaires filled out by the patient during routine visits are used. For any adverse events that occur, information is directly obtained from the patient. In case a patient is seen by more than one physician for his/her disease (e.g. the patient is monitored by a physician other than the initial investigator), the initial investigator should make every effort to collect information on any visits (including results) that have taken place outside the investigator's site due to the patient's disease, for example by interviewing the respective physician or patient or by obtaining an accompanying letter with detailed information and results.

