11.2 Collection

Starting with the first application of Radium-223, all non-serious adverse events (AE) must be documented on the AE Report Form or in the CRF / EDC system using the NCI-CTCAE version 4.03 and forwarded to the sponsor within 7 calendar days of awareness. All serious AEs (SAE) must be documented and forwarded immediately (within 24 hours of awareness).

If a pregnancy occurs during the study (exposition via the father), although it is not a serious adverse event, it should be documented and forwarded to the sponsor within the same time limits as a serious adverse event. The result of a pregnancy will be followed-up according to applicable Bayer SOPs. Any data on abnormal findings concerning either the mother or the baby are collected.

For each AE, the recruiting physician must assess and document the seriousness, duration, relationship to product, action taken and outcome of the event.

The documentation of any AE / SAE ends with the completion of the treatment phase of the patient including 30 days after the last administration of Radium-223.

As long as the patient has not received any Radium-223 AEs /SAEs do not need to be documented as such in this observational study. However, they are part of the patient's medical history.

For any serious drug-related AE occurring after the treatment phase plus 30 days, the standard procedures that are in place for spontaneous reporting have to be followed.

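### Adverse events count up to 30 days after the last injection, but after the last treatment visit only a conditional visit asks about them, so late, mainly non-serious events can be missed

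*Protocol*

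**What the plan says.** Section 8.2 sets the safety objective as "Treatment-emergent adverse events (TEAE) (up to 30 days after last administration of Radium-223". Section 11.2 closes collection at the same point: documentation "ends with the completion of the treatment phase of the patient including 30 days after the last administration of Radium-223".

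Section 9.2.7 describes the visit that would cover this last stretch: "If within routine clinical practice, data will be collected from a follow-up visit approximately one month after end of treatment". Its item list includes "Adverse events up to 30 days after last treatment", and the Table 2 footnote for that cell reads "Up to 30 days after last treatment with Radium-223".

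The next contact is the long-term follow-up, for which "either the patient or treating physician can be contacted by phone, mail or email every three months after end of treatment". Its listed items are date, survival status, opioid use, symptomatic skeletal events and further anti-cancer therapy. Table 2 leaves the adverse-event row blank for long-term follow-up and for end of observation.

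Two further rules apply. Section 9.4 says "For any adverse events that occur, information is directly obtained from the patient" and asks the investigator to pursue information from disease-related visits elsewhere. Section 11.2 requires every adverse event from the first application onward to be documented and forwarded, within 7 calendar days of awareness if non-serious and within 24 hours if serious.

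**The concern.** The endpoint window and the collection schedule do not match. The window extends 30 days past the last injection, but the last contact at which every treated patient is due to be asked about adverse events is the last treatment visit, on the day that stretch begins. The reporting deadlines in Section 11.2 run from awareness: they govern how fast a known event is forwarded, and do not make anyone ask. The protocol does ask about skeletal events and first opioid use at the long-term contacts, so for those outcomes it does not rely on awareness alone.

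At stake is the incidence of treatment-emergent and drug-related events (Section 9.7.5) in a study declared a post-authorization safety study. Under Section 9.7.1, analyses outside pain and quality of life use everyone with at least one dose unless otherwise defined. If the analysis plan adds nothing, a patient who was never asked about the last window counts as event-free for it. The gap is also uneven, because it covers a larger part of the window for patients who received few injections. Blood counts are scheduled at the same conditional visit, so changes in them after the last injection may go unmeasured too.

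**Working it through.** The protocol gives no figure on this point to reproduce. The check compares the contacts and then illustrates the exposure.

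**1. Who asks about adverse events, and when** (Section 9.2.7 and Table 2)

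- Baseline and further treatment visits: adverse events listed.
- Follow-up visit at about one month: listed, up to day 30, but only if the visit is part of routine practice.
- Long-term contact every three months: not listed. It may be with the treating physician instead of the patient.
- End of observation: not listed. Reason for ending is recorded, and in case of death its date and primary cause.

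Without the conditional visit, no scheduled contact asks about days 0 to 30 after the last injection.

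**2. Other routes into the database**

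- Awareness-based reporting of all adverse events to day 30 (Section 11.2).
- Information from disease-related visits elsewhere (Section 9.4).
- Skeletal events and deaths, collected regardless of the conditional visit.

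What these leave open is mainly non-serious events that the patient does not bring to a physician, and unmeasured blood counts.

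**3. Share of TEAE time after the last injection**

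Inputs: typical spacing of four weeks (Section 9.2.7) and a 30-day tail (Sections 8.2 and 11.2). Six injections is the number in the phase III trial described in Section 7 and is used only as an illustration. For k injections the window is 28(k − 1) + 30 days and the tail share is 30 / [28(k − 1) + 30].

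- k = 6: 30/170 = 18%
- k = 3: 30/86 = 35%
- k = 2: 30/58 = 52%
- k = 1: 30/30 = 100%

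These are shares of risk time, not of missed events.

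**4. Possible effect on a recorded incidence (illustration only)**

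Let m be the fraction of patients without the visit and u the fraction of their tail events still captured by other routes. The protocol gives neither, so both are assumptions. Assume a constant hazard and six injections. With true incidence P over 170 days, the incidence by day 140 is P140 = 1 − (1 − P)^(140/170), and the recorded incidence is P − m(1 − u)(P − P140). For P, take two phase III percentages from Section 7: 6% (grade 3/4 thrombocytopenia) and 56% (any grade 3/4 event).

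- P = 6%: P140 = 4.97%. With m = 30%, recorded 5.7% at u = 0 and 5.85% at u = 0.5. At u = 0, m from 10% to 50% gives 5.9% to 5.5%, and m = 100% gives 5.0%.
- P = 56%: P140 = 49.1%. With m = 30%, recorded 53.9% at u = 0 and 55.0% at u = 0.5. At u = 0, m from 10% to 50% gives 55.3% to 52.6%, and m = 100% gives 49.1%.
- At u = 1 there is no loss at any m.

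After a single injection all the time lies in the tail, so the recorded incidence is 1 − m(1 − u) times the true one. With m = 30% that is 70% of the truth at u = 0 and 85% at u = 0.5. The effect is modest for patients with full treatment and can be larger for early stoppers.

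**The case against.** The strongest reply is that collection does not hang on visits. Section 11.2 imposes a standing duty to document every known adverse event to day 30, with a separate report form available, and Section 9.4 tells the investigator to pursue visits elsewhere. Deaths and skeletal events are captured anyway. This stands, and it limits the gap largely to non-serious events nobody reports. It does not close the gap, because the duty starts only once someone knows of the event.

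A reader might infer that toxicity which makes a patient stop treatment is the toxicity most likely to be lost. The documents do not support that. A physician who stops for toxicity is aware of it, the reporting duty then applies, and reasons for discontinuation are to be documented (Section 9.3.6) and summarised (Section 9.7.3). What such a patient can lose is any further event after that decision. He may also attend a planned visit without being injected and have events recorded there, although the protocol does not say how such a visit is classified.

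It is also fair that the treatment of incomplete windows in the denominator may be settled in the analysis plan, and that a patient whose event was recorded earlier is unaffected in a per-patient incidence. But an analysis plan cannot supply events that were never asked about.

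Finally, the conditional visit is deliberate: Section 10.1 excludes additional diagnostic or monitoring procedures. That rules out making the visit mandatory, but not adding a question to a contact already planned.

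**Conclusion.** The protocol does not guarantee that every patient is asked about adverse events between the last injection and day 30. This creates a risk of differential under-ascertainment, mainly of non-serious events, and greater in patients who stop early. The exposure is 18% of TEAE time after six injections, rising to 100% after one, assuming 28-day spacing.

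A reader might go further and conclude that toxicity after the last injection is under-counted. That cannot be said from the documents. They give neither the share of patients without the visit nor the completeness of awareness-based reporting. An assumed 20% to 50% without the visit would be 60 to 150 of 300 patients, but that is only the assumption multiplied out. The bias is nil if awareness-based reporting is complete. TEAEs are one of fourteen secondary objectives in a descriptive single-arm study. The point is worth correcting because the remedy is cheap and the study is a declared safety study; it does not undermine the design.

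**What to change.** In Section 9.2.7 and Table 2, add an adverse-event item to the first long-term contact for every patient who had no follow-up visit on or after day 30. It should cover the period up to 30 days after the last injection and record start date, seriousness, grade, relationship and outcome. It should be put to the patient where possible, since Section 9.4 names the patient as the source and the contact may otherwise be with the physician only. Report the TEAE table with the number of patients whose adverse-event status was ascertained to day 30.

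The cost is one extra eCRF section at a telephone, mail or email contact already planned, with no added visit or procedure, so the study stays non-interventional. The downside is recall: a contact at about three months comes about two months after the window closes, and mild events will be remembered less well. The remedy is therefore partial, and the ascertainment count lets the reader see how far it reached.

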9.1.2 Secondary endpoint(s)

The secondary endpoints are:

- **Changes of pain over time** by evaluating the worst pain item as well as the subscale scores for pain severity and pain interference as determined by patient responses on the BPI-SF questionnaire. The worst pain item and subscales will be presented separately for each post-baseline assessment.
- **Changes in bone pain related quality of life** as determined by patient responses on the bone pain specific FACT-BP questionnaire. The FACT-BP score will be presented separately for each post-baseline assessment.
- **Pain control rate** as determined by the worst pain item on the BPI-SF patient questionnaire. Pain control is defined as no increase by two points from the baseline BPI-SF worst pain score.
- **Pain progression rate** as determined by the worst pain item on the BPI-SF patient questionnaire. Pain progression is defined as an increase by two points from the baseline BPI-SF worst pain score at any post baseline assessment.
- **Time to first pain progression** is defined as the time between the first injection of Radium-223 until an increase in the BPI-SF worst pain item by at least two points.
- **Time to first opioid use** in patients who did not take opioids at study entry is defined as the time from first injection of Radium-223 until first intake of opioid analgesics.
- **Evaluation of covariates on pain response** of mCRPC patients during treatment with Radium-223. The following covariates will be analyzed:
 - opioid use
 - assessment of extent of bone metastases (<6, 6-20, > 20, superscan)
 - location of bone metastases
 - level of alkaline phosphatase at baseline (<150 mU/l, 150-300 mU/l, and >300 mU/l)
 - PSA level at baseline (<50 µg/l, 50-200 µg/l, and >200 µg/l)
 - WHO pain score at baseline (WHO-Score 0+1 and WHO-Score 2+3)
 - pretreatment with chemotherapy (yes/no)
 - pretreatment with deep androgen ablation by treatment with abiraterone or enzalutamide (yes/no)
 - extent of bone uptake in known lesions (only faint, higher uptake, and strong uptake compared to surrounding bone)

- **Relation between bone uptake in known lesions and pain palliation** (only in patients with bone scan prior to start of treatment and a second scan during or within 6 weeks after end of Radium-223 treatment)
- For **Radium-223 treatment patterns** dosage and number of injections of Radium-223 will be analyzed.

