9.3.5 Prior and concomitant medication

All medication taken in addition to the product for any indication (either initiated before study start or during the study) is termed concomitant medication.

Information to be collected for medication except for opioid use includes: trade name or INN, start date, stop date/ongoing, total daily dose, unit, and indication.

Opioid use will be documented on a separate form. Information to be collected include trade name or INN, start date, stop date/ongoing, dose, unit, frequency, application route. In addition, the use of pain medication within 24 h of completing the BPI-SF will be collected.

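### The long-term opioid question is limited to patients without undated prior use, which need not match the time-to-first-opioid population defined by status at entry

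*Protocol*

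**What the plan says.** Section 9.1.2 defines the endpoint "in patients who did not take opioids at study entry" as "the time from first injection of Radium-223 until first intake of opioid analgesics". Membership is decided by status at one moment, study entry. A patient who used opioids earlier and had stopped by then is included. Any opioid analgesic counts; no reason for taking it is required.

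Section 9.2.7, under long-term follow-up, lists "Opioid use after last administration of Radium-223 yes/no, if yes", followed by "date of first use (only in patients without prior opioid use"). These contacts occur every three months for at most two years after treatment.

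Table 2 in section 9.3 lists the same item, and its footnote reads "Only opioid use yes/no and date of first use". It names no subgroup.

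Section 9.3.5 lists the fields for medication other than opioids: "Information to be collected for medication except for opioid use includes: trade name or INN, start date, stop date/ongoing, total daily dose, unit, and indication". For the separate opioid form it says: "Information to be collected include trade name or INN, start date, stop date/ongoing, dose, unit, frequency, application route". Indication is in the first list and not in the second.

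**The concern.** The endpoint and the item that feeds it after treatment describe their patients differently. One uses status at entry. The other uses prior use with no reference time. They part company for former users: men who took opioids at some point, stopped before the first injection, and so are at risk for the endpoint.

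A site that applies section 9.2.7 literally would skip the question for these men, or record a yes without a date. Either way no event time exists after the end-of-treatment visit. A statistical analysis plan can set a censoring rule, but it cannot recover an answer that was never requested. At 8 to 10 patients per site (section 9.2.6), 300 patients means about 30 or more sites, so different readings are likely. A blank could then not be told apart from true absence of opioid use.

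A smaller, separate matter is the missing indication. Without it, opioids taken for bone pain cannot be analysed apart from those taken for other reasons. In long-term follow-up the product is not recorded either, so it cannot be confirmed there that the drug was an analgesic.

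**Working it through.** The protocol gives no event count, rate or precision for this endpoint, so there is no stated figure to reproduce. The check compares the texts and then runs two scenarios.

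**Step 1. Who is asked, under each reading of the parenthesis**

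| Reading | Effect on the endpoint |
|---|---|
| Prior = documented before the last injection, during the study | None lost: these patients were on opioids at entry (outside the endpoint) or have already had the event |
| Prior = any earlier use, including use stopped before entry | Former users are in the endpoint but not asked |
| Restriction applies only to the date | Former users are asked yes/no, but a yes has no date and gives no event time |
| Table 2 footnote as written | All asked and dated; none lost |

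The text does not choose between these readings.

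**Step 2. Events at stake if prior means any earlier use**

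Events lost = 300 × q × f × e. N = 300 is from section 9.1. The rest are assumptions: q = share opioid-free at entry (0.4 to 0.6), f = share of those who are former users (0.05 to 0.30), e = probability of a first on-study opioid during long-term follow-up (0.2 to 0.4).

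- Low: 300 × 0.4 × 0.05 × 0.2 = 1.2 of 300 × 0.4 × 0.2 = 24 events.
- High: 300 × 0.6 × 0.30 × 0.4 = 21.6 of 300 × 0.6 × 0.4 = 72 events.

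The fraction of long-term events lost equals f.

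**Step 3. Effect on the 24-month estimate**

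Assumptions, none in the protocol: exponential times to opioid; median 6 months in former users and 14 months in the others; no deaths; former users' opioid data end 5.6 months after the first injection (six injections four weeks apart, 20 weeks = 4.6 months, plus one month to the follow-up visit).

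Opioid-free probabilities, S(t) = 0.5^(t/median):

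- Former users: S(24) = 0.5^(24/6) = 0.0625; S(5.6) = 0.5^(5.6/6) = 0.5236.
- Others: S(24) = 0.5^(24/14) = 0.3048; S(5.6) = 0.5^(5.6/14) = 0.7579; S(24)/S(5.6) = 0.4021.

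True cumulative use = 1 − [f × 0.0625 + (1 − f) × 0.3048].

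Kaplan-Meier with former users censored at 5.6 months = 1 − [f × 0.5236 + (1 − f) × 0.7579] × 0.4021.

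| f | True | Former users censored | Gap |
|---|---|---|---|
| 0.10 | 0.7195 | 0.7047 | 0.0148 |
| 0.20 | 0.7437 | 0.7141 | 0.0296 |
| 0.30 | 0.7679 | 0.7235 | 0.0444 |

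The gap is about 1.5 to 4.5 percentage points. It arises only because former users are assumed to restart sooner. With equal rates in both groups, censoring them would cost precision but would not bias the estimate.

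**The case against.** The strongest reply is that the item concerns use after the last injection, so prior can naturally mean use already documented by then, and nothing is lost. Table 2 carries no restriction, which supports collecting the item from everyone. The list in section 9.2.7 is headed as typical information, and the case report form is a separate document not available when the protocol was written, so what sites are actually asked cannot be known from here. All of this stands. A reader might infer that former users' later events are lost by design; the documents do not support that. They support an undefined term that permits such a loss, in a protocol that describes the item in two ways.

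On size, a reader might also infer a much larger bias. If former users were carried forward as event-free, the f = 0.20 case would give 1 − [0.20 × 0.5236 + 0.80 × 0.3048] = 0.65 against a true 0.74. The protocol prescribes no such handling. Even the censored gaps are below sampling error: with an assumed 150 patients at risk, the 95% half-width at 74% is 1.96 × √(0.74 × 0.26/150) = 0.070, even with complete follow-up.

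On indication, a reader might infer that opioids taken for reasons other than cancer pain are counted wrongly. They are not: the definition counts any opioid analgesic. During treatment the recorded name and route also allow some non-analgesic products to be excluded. What remains is limited specificity, mainly in long-term follow-up.

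**Conclusion.** The point holds as an inconsistency between the endpoint population in section 9.1.2, the long-term item in section 9.2.7 and the Table 2 footnote. If sites take prior as any earlier use, former users' later opioid intake may go unasked or undated. Time to first opioid use is then biased upward, provided these men restart sooner than the rest. The amount cannot be determined from the protocol. The figure of about 1.5 to 4.5 points at 24 months rests on assumed former-user shares of 10 to 30%, assumed medians of 6 and 14 months, no deaths and ordinary censoring. It is zero if prior means use documented during the study.

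The absent indication is not an error against the stated definition; it only prevents a supportive analysis by reason for use. The endpoint is one of many secondary, descriptive ones. The correction is still worth making because it is cheap, and data not requested cannot be restored later.

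**What to change.** In section 9.2.7, replace the parenthesis with: in all patients not taking opioids at the first Radium-223 injection and with no opioid intake documented since. Add the same population to the Table 2 footnote, which at present states none.

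Optionally, add indication to the opioid form in section 9.3.5, and product plus indication to the long-term item. Keep the stated event, first opioid analgesic for any reason, as the main analysis, and report opioids taken for cancer or bone pain as a supportive analysis.

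The cost is one reworded parenthesis, one extended footnote, one extra question for former users and, if the option is taken, one or two further eCRF fields, all at contacts already planned.
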